In this proposed study we plan to recruit patients with type 2 diabetes of ≤ 15 years duration (in early phase of diagnosis), who are on a stable dose of insulin, Metformin, or both for at least 3 months either short or long acting but still remain inadequately controlled with HbA1C between 6.5% and 10% (both values inclusive), but not overtly out of control ($> 10\%$ of HbA1C).

The patient will adjust insulin levels so as to keep their HbA1C levels under 10.0%, for health measures. If the HbA1c rises above 10.0% then the PI will speak with the patient and provide a documented form indicating the insulin dose adjustment that should be

made. Initially life-style intervention with diet and regular aerobic activity (as per Standards of Diabetes Care: Diabetes Care Supplement: Jan 2014) along with insulin titration will be undertaken for initial 4 weeks (time between screening visit and 1st visit). Subjects will begin taking 5.0 mg of Linagliptin or placebo after initial 4 weeks. Subjects will be withdrawn from the study if the medication or placebo is not tolerated.

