3 INVESTIGATIONAL PLAN

3.1 Study Design and Duration

Study Schema, 40 Type 2 diabetic Subjects Aged 40-70 on stable dose of Insulin, Metformin, or both

+/- 3 day window for visits

*Assessed at week 0, 6 and 12: Biochemical and cellular markers of endothelial function and Pulse wave analysis and velocity (PWA and PWV), REE and Adiposity.

Week 16 - A telephone call to subjects will be made 30 days after last dose of study medication to determine if there have been any adverse events.

Available related studies and Expected Results: Studies measuring changes to EPCs in type 2 diabetes patients are very limited. To the best of our knowledge there are no studies examining the effect of Linagliptin in type 2 diabetes patients with CKD.

Use of CD34 positive cells as a cardiovascular risk surrogate has been reported in the past. Various studies (11, 34), have shown that various disease states, including those seen in diabetes, can deplete and damage EPC, thereby diminishing their regenerative potential. The inability to maintain or repair damaged endothelial tissue leads to cumulative vascular dysfunction and cardiovascular disease.

We hypothesize that monitoring **number, function and gene expression of endothelial progenitors will allow us to quantify cardiovascular disease risk at the onset and regenerative potential post intervention at a cellular level. It will also help us to identify and correlate the best endothelial function bio-chemical inflammatory marker as an early indicator of cardiovascular disease progression in early type 2 diabetes with CKD and identify patients that are responders.**

Linagliptin along with other gliptins can increase SDF1 alpha levels and possibly CXCR4 receptor expression which will help EPC mobilization and gene expression of hemopoietic CD34 positive stem cells.

Linagliptin 5 mg or placebo will be added to patients who have type 2 diabetes diagnosed ≤ 15 years with HbA1C of 6.5 to 10 % (both inclusive) while being on Insulin, metformin, or both.

Insulin will be titrated upwards if HbA1C is above 10% with minimal dose adjustments so as to keep the adjusted HbA1C below overtly uncontrolled levels (above 10%).

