A serious adverse event (SAE) is defined as any AE which results in death, is immediately life-threatening, results in persistent or significant disability / incapacity, requires or prolongs patient hospitalisation, is a congenital anomaly / birth defect, or is to be deemed serious for any other reason if it is an important medical event when based upon appropriate medical judgement which may jeopardise the patient and may require medical or surgical intervention to prevent one of the other outcomes listed in the above definitions. Patients may be hospitalised for administrative or social reasons during the study (e.g. days on which infusion takes place, long distance from home to site,). These and other hospitalisations planned at the beginning of the study do not need to be reported as a SAE in case they have been reported at screening visit in the source data and have been performed as planned.

“Adverse Events of Special Interests” or “AEs of Special Interest” shall include:

1. Severe Allergic Reactions
2. Skin changes
3. Angio-edema
4. Heart attack or cerebral attack
5. Neurological manifestations
6. Acute Pancreatitis or acute hepatic failure
7. Acute worsening of renal function
8. Development of malignancy, occult or overt
9. Severe Documented Hypoglycemia (lab blood sugar less than 40mg%)

AEs of special interest are a list of medical topics that are under close surveillance. AE should be reported in an expedited manner similar to Serious Adverse Events even if they do not meet the seriousness criteria.

Please refer to the site master file for the complete list of AESIs (27-30).

Intensity of adverse event

The intensity of the AE should be judged based on the following:

- Mild: Awareness of sign(s) or symptom(s) which is/are easily tolerated
- Moderate: Enough discomfort to cause interference with usual activity
- Severe: Incapacitating or causing inability to work or to perform usual activities

Causal relationship of adverse event

Medical judgment should be used to determine the relationship, considering all relevant factors, including pattern of reaction, temporal relationship, de-challenge or re-challenge, confounding factors such as concomitant medication, concomitant diseases and relevant history. Assessment of causal relationship should be recorded in the case report forms.

Yes: There is a reasonable causal relationship between the investigational product administered and the AE.

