4.5 Study Schematic. Time and Events Schedule

Time and Events Schedule for Protocol

Procedure	Screening Visit (Week -4)	Baseline/ Randomization Visit 1 (Week 0)	During Treatment Visit 2 (Week 6)	End-of- Treatment Visit 3 (Week 12)	Follow up phone call (week 16)
Eligibility Assessments					
Informed Consent	X				
Inclusion/Exclusion Criteria	X				
Medical History	X				
Safety Assessments					
Physical Examination	X			X	
Targeted Physical Examination (as needed)		X	X	X	
Vital Signs	X	X	X	X	
Assessment of Signs and Symptoms		X	X	X	
Adverse Events Assessment	X	X	X	X	X
Laboratory Tests (Biochemical)	screening	X	X	X	
Urine Pregnancy (If needed)	X	X	X	X	
Spot Urine Sample	X	X	X	X	
Tanita Scale Body Composition		X	X	X	
Waist / Hip		X	X	X	
Efficacy Assessments					
Peripheral blood draw for CD34+cell harvest		X	X	X	
Pulse wave analysis and Pulse wave velocity assessment		X	X	X	
RMR		X	X	X	
Clinical Drug Supplies					
Randomize		X			
Dispense Study Treatment		X	X		

Screening visit= week-4; Visit 1= week 0, Visit 2= week 6 and Visit 3= week 12.

Research Study Design and Methods:

Patient Definition and Selection: Adults aged 40-70 years will be recruited from the GWU MFA research patient database provided by MFA Information Technology, and then contacted via email and phone, from the endocrinology and other provider clinics at GWU and through referrals from the Veterans Affairs (VA) clinics. Suitable advertisements for the study patient enrollment will be posted. Patients will be included in the study if they have been diagnosed with type 2 diabetes within the previous 15 years using criteria of the American Diabetes Association (2), and are currently treated with a stable dose of Insulin, Metformin, or both. We plan to enroll subjects with HbA1C between 6.5% and 10% (both inclusive) and with BMI 25-39.9 kg/m² (both inclusive). Post enrollment, patients will be randomized to Linagliptin 5 mg or placebo as detailed in Study Design for direct comparison between the two regimens.

Before any study procedures are performed, subjects will have the details of the study described to them, and they will be given a written informed consent document to read. Then, if subjects consent to participate in the study, they will indicate that consent by signing and dating the informed consent document in the presence of study personnel.

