As per recent clinical guidelines (2), all patients at entry will receive dietary advice by study coordinator, diabetes educator, or registered dietician specifically geared towards type 2 diabetes patients. They will be advised to adhere to 150 minutes of weekly aerobic exercise (50-70% of maximal heart rate). Patient's activity will be monitored using accelerometers and will be downloaded at visit 2 and visit 3 by the study staff.

Subjects will be taking 5.0 mg of Linagliptin or placebo. Dose titration of insulin will be allowed so that the HbA1C is maintained below 10%.

Visits with outcome measurements will be scheduled for the morning while overnight fasting (except water) to reduce diurnal variability, and clinical parameters will be obtained at scheduled office visits as depicted in the study schema and will be measured at each outcome visit as follows:

Week -4: Subjects will be screened and eligibility will be verified based on physical and laboratory tests. Equal numbers of male and female patients will be recruited. All patients will be educated on the recommended lifestyle changes of maintaining a level of aerobic activity of 150 minutes/ week (non-supervised) and adherence to a healthy diet as advised by the study coordinator, a diabetes educator, or a dietitian as part of the type 2 diabetes patient management plan [2]. We will allow 4 weeks for the patients to reach a steady state while implementing diet and exercise changes.

Week 0: At this stage patients will be randomized into the study. Subjects will have the first set of measurements. We will make sure that patients still meet the inclusion criteria. They will be started on medication or placebo and will be encouraged to continue 150 minutes/week of moderate physical exercise and dietary management for the remainder of the study.

Weeks 0, 6 and 12: Subjects will all have the same measurements and will continue on study medication or placebo. All primary and secondary measures as outlined before will be carried out.

The cellular outcome measures are as follows:

From MNC population (pre magnetic column sorting):

A. FACS Analysis, 1 million cells in each tube/assay column. 12 tubes-- total 12 million. (All labelling antibodies are obtained from Miltenyi Biotec except Sytox blue-Invitrogen and anti-VEGFR2/KDR-R&D systems)

1. Unlabelled

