4.8 Safety Assessments

Study drug toxicities will be assessed continuously. Adverse events will be evaluated on a continuous basis while the patient is on study and until 30 days after the last dose of study drug. Patients should be followed until all treatment-related adverse events have recovered to baseline or are deemed irreversible by the principal investigator.

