To estimate the effect of linagliptin on CD34+/KDR+ cells, we originally proposed a sample size of 20 per group in 2 groups, giving us power = .73, assuming alpha=.05, between time points of .60 and equal allocation between groups. Thus, the group x time interaction effect size we were modeling was an interaction that explained 3% of total variance, or a partial eta-square = .0291. Using 3 groups (Insulin only, metformin only, metformin + insulin), with the same effect size, we would achieve this same level of power using a total sample size of 51 (17 per group). However, given the relatively small numbers of potential participants with insulin-only (n=21) and insulin+metformin (n=54), and the relative large number with Metformin only (260), we will need to change the allocation ratio between groups. Maintaining the same total sample size as originally proposed (40), we will allocate patients from each group in the following numbers: **Metformin only (22), Metformin+insulin (12), Insulin only (6)**. We recognize that we will be underpowered for comparisons between the Metformin + insulin versus Insulin groups. However, comparisons with the Metformin-only group will still have reasonable power. Given the small number of potential patients with Insulin-only, this is a feasible strategy for including this group in the analysis.

Data Analysis.

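### Severe hypoglycaemia is an event of special interest only with a laboratory glucose, and the plan describes no way to obtain one between visits, so severe episodes at home can miss expedited reporting

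*Combined protocol and SAP*

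**What the plan says.** The AESI list in Section 4.4 has nine items. The ninth reads "Severe Documented Hypoglycemia (lab blood sugar less than 40mg" per cent). It is the only item on the list that states a laboratory threshold. AESIs are to be reported in an expedited manner like serious adverse events, whether or not they are serious. They go to the manufacturer on its serious-event form. For the complete list, the section refers to the site master file.

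The same section grades the intensity of any adverse event. An event is severe if it incapacitates the patient or prevents work or usual activities. No laboratory test is involved.

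The note under the schedule in Section 4.5 gives the visits: "Screening visit= week-4; Visit 1= week 0, Visit 2= week 6 and Visit 3= week 12". Section 3.1 agrees on the sampling times: "Assessed at week 0, 6 and 12: Biochemical and cellular markers of endothelial function". Of patients at week 0, Section 4.5 says: "They will be started on medication or placebo". It also says: "Visits with outcome measurements will be scheduled for the morning while overnight fasting". Week 16 is a telephone call.

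On exposure to the risk, Section 5 allocates "Metformin only (22), Metformin+insulin (12), Insulin only (6"). Section 1 says: "The patient will adjust insulin levels so as to keep their HbA1C levels under 10.0%, for health measures". Section 4.5 allows insulin titration and advises 150 minutes of aerobic exercise a week.

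The separate AESI guidance document after Appendix A names eight topics. Hypoglycaemia is not one of them.

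**The concern.** An AESI label is meant to bring an event to attention quickly even when it is not serious. Here the label depends on a measurement that the plan takes twice on treatment, in the morning after an overnight fast. Hypoglycaemia is often handled where it happens, by the patient or someone nearby, with a meter at most. The plan issues accelerometers to follow activity between visits but describes nothing comparable for glucose.

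At stake is whether severe episodes reach expedited review, and whether a tally of item 9 can be read as a tally of severe hypoglycaemia. Nearly half the patients are to be on insulin, and one arm receives an additional glucose-lowering drug.

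**Working it through.** The plan states no figure on this point, so there is none to reproduce. The check compares the definition with the means of meeting it.

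**Scheduled laboratory coverage on treatment**
- Treatment lasts 12 weeks (Section 3.1): 12 × 7 = 84 days.
- The schedule marks laboratory tests at screening and at weeks 0, 6 and 12. Drug starts at week 0, at the visit with the first set of measurements, so that sample is the baseline. On-drug samples: 2.
- Days with a scheduled sample: 2/84 = 2.4%. Days without: 82/84 = 97.6%.
- The visit window of plus or minus 3 days moves these samples but adds none. The week-16 call adds none.

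**Patients on insulin (Section 5)**
- Metformin plus insulin 12, insulin only 6: 12 + 6 = 18, and 18/40 = 45%.

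**Item 9 applied to hypothetical episodes**

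| Episode | Meets item 9? | Otherwise handled as |
|---|---|---|
| Incapacitated at home, helped by a relative, meter reading 35 mg/dL, no laboratory sample | No | Adverse event, intensity severe; expedited only if judged serious or placed under another AESI item |
| Same episode, emergency laboratory glucose below 40 | Yes | – |
| Same episode, treated before blood is drawn, laboratory value above 40 | No | As in the first row |
| Week 6 or 12 laboratory glucose below 40 | Yes | – |

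The first three rows describe the same clinical event. Whether item 9 applies depends on whether, and when, a laboratory sample was drawn. The first and third rows would also be graded severe on the section's own intensity scale, so an episode can be a severe hypoglycaemic adverse event and still fall outside the severe hypoglycaemia AESI.

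**The two AESI lists**
- Section 4.4 includes hypoglycaemia. The guidance document, which asks for non-serious events in its topics on the serious-event form, does not. It therefore offers no second route for the first or third row.

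**The case against.** Much of the case on the other side stands.

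- A reader might infer that events at home cannot meet the definition. The text does not say so: it asks for a laboratory value, not one from a study visit. An episode that starts at home and yields an emergency laboratory glucose below 40 qualifies.
- A reader might take 2.4% as the chance of detecting an event, or expect item 9 counts near zero. The figure is scheduled-sample coverage only. AESIs are reported events, and the documents do not give the share of severe episodes that receive an unscheduled laboratory test.
- A reader might see a contradiction with Section 4.8, which says "Study drug toxicities will be assessed continuously". There is none. The definition of an adverse event has no laboratory condition, so a home episode is assessed and recorded whatever its AESI status.
- Other routes to expedited reporting exist. An episode that leads to hospital admission, is immediately life-threatening or is judged medically important is serious at any glucose value. Neurological manifestations form a separate AESI item with no threshold.
- No planned analysis compares hypoglycaemia between arms, and no figure in the documents shows it to be the risk most likely to differ between them.
- The insulin risk should not be read from Section 1 alone. Section 3.1 speaks of minimal upward adjustments above an HbA1c of 10%, and Section 4.1 of continuing the entry dose. These passages need reconciling by the sponsor, but this point does not depend on the outcome.

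These arguments narrow the point without removing it. The alternative routes depend on a judgement of seriousness or on the choice of another label. An incapacitating episode at home with no laboratory value is still excluded from the item written for it.

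**Conclusion.** The concern holds as a defect of AESI classification and expedited reporting. It is not a failure to record events. As written, item 9 excludes any severe hypoglycaemic episode without a laboratory value below 40 mg%, and the plan describes no means of obtaining a value between visits. On 82 of 84 treatment days no sample is scheduled, and 18 of 40 patients are to be on insulin. The number of episodes affected cannot be estimated from the documents.

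The conclusion assumes that item 9 is applied literally, so that a meter reading does not count as a laboratory value, and that the site master file, which was not available, holds no wider definition. If that file does, the protocol's narrower wording should be brought into line with it. The change is worth making because a stated rule causes the exclusion and the remedy is small.

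**What to change.** These changes concern capture and reporting only. The glucose threshold remains the sponsor's decision.

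1. Reword item 9 so that it also admits hypoglycaemic episodes graded severe on the existing Section 4.4 intensity scale, and non-laboratory meter values that meet the sponsor's own threshold. Keep laboratory-confirmed as a sub-category. Admitting any glucose reading with no severity condition or threshold would be too broad, because it would bring mild episodes into expedited reporting.
2. At the existing adverse-event assessments (weeks 0, 6 and 12 and the week-16 call), ask every patient the same fixed hypoglycaemia question and record any meter readings the patient already has. The week-0 question covers the four weeks before study drug.
3. Reconcile item 9 with the AESI guidance document, which omits hypoglycaemia, and with the list in the site master file.

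The cost is a change of wording and one case report form question, with no added visits or samples. The downside is a few more expedited reports, some without laboratory confirmation, which the sub-category makes visible.

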4.5 Study Schematic. Time and Events Schedule

Time and Events Schedule for Protocol

Procedure	Screening Visit (Week -4)	Baseline/ Randomization Visit 1 (Week 0)	During Treatment Visit 2 (Week 6)	End-of- Treatment Visit 3 (Week 12)	Follow up phone call (week 16)
Eligibility Assessments					
Informed Consent	X				
Inclusion/Exclusion Criteria	X				
Medical History	X				
Safety Assessments					
Physical Examination	X			X	
Targeted Physical Examination (as needed)		X	X	X	
Vital Signs	X	X	X	X	
Assessment of Signs and Symptoms		X	X	X	
Adverse Events Assessment	X	X	X	X	X
Laboratory Tests (Biochemical)	screening	X	X	X	
Urine Pregnancy (If needed)	X	X	X	X	
Spot Urine Sample	X	X	X	X	
Tanita Scale Body Composition		X	X	X	
Waist / Hip		X	X	X	
Efficacy Assessments					
Peripheral blood draw for CD34+cell harvest		X	X	X	
Pulse wave analysis and Pulse wave velocity assessment		X	X	X	
RMR		X	X	X	
Clinical Drug Supplies					
Randomize		X			
Dispense Study Treatment		X	X		

Screening visit= week-4; Visit 1= week 0, Visit 2= week 6 and Visit 3= week 12.

Research Study Design and Methods:

Patient Definition and Selection: Adults aged 40-70 years will be recruited from the GWU MFA research patient database provided by MFA Information Technology, and then contacted via email and phone, from the endocrinology and other provider clinics at GWU and through referrals from the Veterans Affairs (VA) clinics. Suitable advertisements for the study patient enrollment will be posted. Patients will be included in the study if they have been diagnosed with type 2 diabetes within the previous 15 years using criteria of the American Diabetes Association (2), and are currently treated with a stable dose of Insulin, Metformin, or both. We plan to enroll subjects with HbA1C between 6.5% and 10% (both inclusive) and with BMI 25-39.9 kg/m² (both inclusive). Post enrollment, patients will be randomized to Linagliptin 5 mg or placebo as detailed in Study Design for direct comparison between the two regimens.

Before any study procedures are performed, subjects will have the details of the study described to them, and they will be given a written informed consent document to read. Then, if subjects consent to participate in the study, they will indicate that consent by signing and dating the informed consent document in the presence of study personnel.

Recruitment: Subjects will be recruited from the physician clinics at GWU, Medical Faculty Associates, where [name] is a clinician, as well as through referral from the VA. All patients will receive counseling regarding the study aims and methods.

Study Design Overview: We propose a 2-arm randomized, double-masked, placebo-controlled, parallel group, longitudinal study of 12-weeks duration. (See study design below), recruited over 3 years. The 12 week time interval has been previously shown adequate to observe changes in endothelial progenitor stem cells, biochemistry and importantly, PWV changes [20, 36]. Patients will be randomized to 2 groups:

Control, (n=20), Insulin/Metformin/Both + Lifestyle + Placebo

Treatment, (n=20) Insulin/Metformin/Both + Lifestyle + Linagliptin 5mg

This proposed study is based on patients with type 2 diabetes of ≤ 15 years duration, who are on stable dose of insulin, Metformin, or both for at least 3 months but still remain poorly controlled with HbA1C between 6.5% and 10% (both inclusive), but not overtly out of control ($> 10\%$ of HbA1C). Our study design is similar to that of Fadini et al [20] where Sitagliptin was compared to placebo with endothelial progenitor cells as an outcome measure in patients with type 2 diabetes over 4 weeks.

Though our study is over 12 weeks we do not anticipate significant drop in HbA1C in between the two groups in this relatively short time period to act as a confounding factor on CD34+ cell number, function and gene expression.

Most clinical studies looking at HbA1C reduction were of a much longer duration of 6 months or above and most DPP-4 inhibitor studies are with animal EPCs where comparison with human CD34+ population is difficult to make. In one study (58) where saxagliptin was used for **12 weeks** in drug-naïve type 2 diabetes patients there was placebo-subtracted HbA1c reduction noted of 0.45-0.63%. It showed mean placebo-subtracted reductions in fasting serum glucose of 20 mg/dL. From our laboratory studies of in vitro human EPC studies we do not think glucose level change of 20 mg/dL is significant enough to account for changes in EPC number, function and gene expression. However we will take the possibility of glycemia change/ reduction in experimental arm into account during statistical analysis of the results between the Linagliptin and placebo groups.

As per recent clinical guidelines (2), all patients at entry will receive dietary advice by study coordinator, diabetes educator, or registered dietician specifically geared towards type 2 diabetes patients. They will be advised to adhere to 150 minutes of weekly aerobic exercise (50-70% of maximal heart rate). Patient's activity will be monitored using accelerometers and will be downloaded at visit 2 and visit 3 by the study staff.

Subjects will be taking 5.0 mg of Linagliptin or placebo. Dose titration of insulin will be allowed so that the HbA1C is maintained below 10%.

Visits with outcome measurements will be scheduled for the morning while overnight fasting (except water) to reduce diurnal variability, and clinical parameters will be obtained at scheduled office visits as depicted in the study schema and will be measured at each outcome visit as follows:

Week -4: Subjects will be screened and eligibility will be verified based on physical and laboratory tests. Equal numbers of male and female patients will be recruited. All patients will be educated on the recommended lifestyle changes of maintaining a level of aerobic activity of 150 minutes/ week (non-supervised) and adherence to a healthy diet as advised by the study coordinator, a diabetes educator, or a dietitian as part of the type 2 diabetes patient management plan [2]. We will allow 4 weeks for the patients to reach a steady state while implementing diet and exercise changes.

Week 0: At this stage patients will be randomized into the study. Subjects will have the first set of measurements. We will make sure that patients still meet the inclusion criteria. They will be started on medication or placebo and will be encouraged to continue 150 minutes/week of moderate physical exercise and dietary management for the remainder of the study.

Weeks 0, 6 and 12: Subjects will all have the same measurements and will continue on study medication or placebo. All primary and secondary measures as outlined before will be carried out.

The cellular outcome measures are as follows:

From MNC population (pre magnetic column sorting):

A. FACS Analysis, 1 million cells in each tube/assay column. 12 tubes-- total 12 million. (All labelling antibodies are obtained from Miltenyi Biotec except Sytox blue-Invitrogen and anti-VEGFR2/KDR-R&D systems)

1. Unlabelled
